4.4.2. Reasons for Discontinuation of Investigational Product

Any subject experiencing the following will be required to discontinue investigational product:

AE:

Pancreatitis, acute or chronic.

Pancreatic cancer.

MTC or other thyroid C-cell neoplasia. In subjects where a treatment emergent thyroid nodule is identified, if serum calcitonin is measured at the discretion of the Investigator (e.g., per local guidelines) and found to be >100 ng/L this should prompt further investigation for MTC and potential interruption or discontinuation of investigational product until diagnosis has been resolved.

Liver chemistry abnormalities exceeding the threshold criteria outlined in Section [4.4.3](#)

Severe allergic/hypersensitivity reactions that are considered by the investigator to be attributable to investigational product or without a likely alternative aetiology.

Other AE which, in the opinion of the investigator precludes continuation of dosing. eGFR<15ml/min/1.73m² (Section [4.4.4](#)) or the need for renal replacement therapy.

Subject becomes pregnant during the study.

Need for chronic use of a prohibited concomitant medication (Section [5.6.2](#))

Decision by subject or proxy.

Sponsor terminated study.

Investigator site closed and subject was unable to transfer to another investigative site.

[figure not shown]
If investigational product is discontinued, the subject should continue in the study and be followed until the final study visit as detailed in Section [4.5](#).

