Immunogenicity. Hypersensitivity reactions are of potential concern with any injected protein and were reported rarely in the Phase III programme. In the Phase III programme one subject (anti-albiglutide antibody negative) developed rash, itching and dyspnoea. Subjects with known allergy to any GLP-1 receptor agonist or excipients of albiglutide are excluded from the study. Subjects will be informed of the symptoms of severe hypersensitivity or allergy and be advised to seek medical assistance immediately. In the Phase III programme approximately 5% of subjects developed anti-albiglutide antibodies. Subjects who tested positive for anti-albiglutide antibodies experienced a similar glycaemic response (HbA1c and fasting plasma glucose) to those who did not test positive for antibodies. Other than injection site reactions (see below), the overall safety profile appeared similar among the subset of subjects who did and those who did not test positive for anti-albiglutide antibodies. Anti-albiglutide antibody formation is not expected to impact the overall safety of albiglutide treatment and therefore will not be measured routinely in this study.

Injection site reactions. Albiglutide injections may cause rash, erythema or itching and/or other reactions at the site of injection. . Subjects will be advised that when injecting in the same region, to use a different injection site each week. In the Phase III program, most subjects with injection site reactions did not test positive for anti-albiglutide antibodies. However, injection site reactions were reported more frequently among those who did test positive for anti-albiglutide antibodies (41% of the antidrug antibody positive subjects reported one or more injection site reactions) than among those who were consistently antibody negative (14% of the antidrug antibody negative subjects reported one or more injection site reactions).

Other adverse reactions (e.g. pneumonia, atrial fibrillation/flutter, and appendicitis). In the Phase III programme in type 2 diabetes, other possible albiglutide related adverse reactions were identified. These events occurred at a cumulative incidence <3% in studies up to 3 years in duration. These events were reported more frequently with albiglutide than comparators.

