6.2.3. Adverse Events of Special Interest

The investigator or site staff will be responsible for detecting, documenting and reporting events the following AEs of special interest:

Development of thyroid cancer

Haematologic malignancy

Pancreatic cancer

Pancreatitis

Injection site reactions

Immunological reactions (e.g., drug hypersensitivity reactions involving anaphylaxis/anaphylactoid reactions, acute bronchoconstriction, angioedema, and/or acute urticaria)

Severe hypoglycaemia events (which includes all events meeting the definition of SAEs [Appendix 5](#))

Hepatic events

Hepatic enzyme elevations (including GGT)

Serious GI events

Appendicitis

Atrial fibrillation/flutter

Pneumonia

Worsening renal function

Diabetic retinopathy

The results of any investigation should be recorded in the relevant sections of the subjects' eCRFs. In addition, for thyroid, pancreas or haematological malignancies a copy of the histopathology report and a discharge summary if the subject was admitted, or any available case summary (e.g. clinic letter), is to be provided to the Sponsor, if available.

Subjects with treatment emergent thyroid nodules should be referred to a specialist for evaluation in accordance with local treatment guidelines. In subjects where a treatment emergent thyroid nodule is identified, if serum calcitonin is measured at the discretion of the Investigator (e.g., per local guidelines) and found to be >100 ng/L this should prompt further investigation for MTC and potential interruption or discontinuation of

investigational product until diagnosis has been resolved. If MTC or other thyroid C-cell neoplasia is diagnosed, albiglutide will be discontinued.

A Pancreatitis Adjudication Committee composed of independent specialists in gastroenterology will review all cases of possible pancreatitis.

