Subjects should also be closely monitored for signs of potential allergic or drug hypersensitivity reactions including anaphylaxis, angioedema, generalized urticaria, and other potential manifestations of systemic allergic or drug hypersensitivity reactions. A serum sample should be taken as soon as possible after any such event in order to measure antibody to the drug. Instructions for sample processing are in the SRM. These events should be reported as AEs or SAEs based on the clinical evaluation of the subject. The reactions should be followed to completion as typical for any AE or SAE. Subjects with allergic or drug hypersensitivity reactions that are considered by the investigator to be attributable to investigational product or without a likely alternative aetiology should have investigational product withdrawn and not re-introduced.

Episodes of severe hypoglycaemia will be recorded according to subject report. Severe hypoglycaemic incidents will be defined as those episodes of hypoglycaemic symptoms for which the subject required assistance from another person and from which the subject recovered promptly after oral carbohydrate, intravenous glucose, glucagon administration or other resuscitative actions (definition per ADA Workgroup on Hypoglycaemia [Seaquist, 2013]). Additionally, all episodes of hypoglycaemic symptoms which in the investigator's opinion meet the definition of a SAE (defined in [Appendix 5](#)) will be included as severe hypoglycaemic episodes. During this study, if a subject's eGFR approaches 30mL/min/1.73m² closer monitoring of renal function is considered prudent, according to standard clinical practice. If eGRF is <15mL/min//1.73m² follow the procedure set out in Section [4.4.4](#).

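### Section 4.4.2 makes stopping mandatory only for severe attributable hypersensitivity, while Section 6.2.3 calls for permanent withdrawal with no severity limit

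*Protocol*

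**What the plan says.** Section 4.4.2 opens its list with a mandatory instruction: "Any subject experiencing the following will be required to discontinue investigational product". The hypersensitivity item on that list is "Severe allergic/hypersensitivity reactions that are considered by the investigator to be attributable to investigational product or without a likely alternative aetiology". The list also has a general adverse-event item: "Other AE which, in the opinion of the investigator precludes continuation of dosing".

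Section 6.2.3 counts immunological reactions among the adverse events of special interest: "Immunological reactions (e.g., drug hypersensitivity reactions involving anaphylaxis/anaphylactoid reactions, acute bronchoconstriction, angioedema, and/or acute urticaria". Later in the same section, sites are told to monitor closely for allergic and hypersensitivity reactions, "including anaphylaxis, angioedema, generalized urticaria, and other potential manifestations of systemic allergic or drug hypersensitivity reactions". The paragraph ends with the action to take. Subjects whose reactions the investigator considers "attributable to investigational product or without a likely alternative aetiology should have investigational product withdrawn and not re-introduced". No severity is mentioned in that sentence.

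Appendix 5 (Section 11.5.4) grades intensity as mild, moderate or severe. Severe is the grade for an event that stops the subject from carrying on normal daily activities.

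**The concern.** The two sections describe the same safety event and use the same attribution test, but they set different thresholds for stopping. One word in 4.4.2 changes which subjects must come off product.

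Investigators will naturally turn to 4.4.2 when deciding whether a subject has to stop. For hypersensitivity, that section does not send them to 6.2.3. It does point elsewhere for other items: the liver item reads "Liver chemistry abnormalities exceeding the threshold criteria outlined in Section" 4.4.3, and the eGFR and prohibited-medication items refer to 4.4.4 and 5.6.2. A site relying on 4.4.2 alone could conclude that a moderate attributable reaction does not oblige it to stop.

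What is at stake is re-exposure after a systemic reaction attributed to product. Hypersensitivity is discussed under identified risks in Section 3.4.1.1, where such reactions "were reported rarely in the Phase III programme. In the Phase III programme one subject (anti-albiglutide antibody negative) developed rash, itching and dyspnoea". That case is given without a severity grade. A similar attributable reaction in this trial would come under 6.2.3 whatever its grade, but under the named 4.4.2 item only if it was judged severe.

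**Working it through.** No arithmetic applies. The check is a comparison of the two rules in the current text.

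| Element | Section 4.4.2 | Section 6.2.3 |
|---|---|---|
| Attribution test | Attributable to product, or no likely alternative cause | The same |
| Severity limit | 'Severe' only | None stated |
| Force | 'Required' | 'Should' |
| Action | Discontinue | Withdraw and do not re-introduce |
| Re-introduction | Not mentioned | Barred |
| Reference to the other section on this point | None | None |

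There are two cases, both with the attribution test met:

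1. **Severe reaction.** Section 4.4.2 requires a stop. Section 6.2.3 calls for a stop and adds that product is not given again. The two agree on stopping.
2. **Mild or moderate reaction, for example generalized urticaria.** The named item in 4.4.2 does not apply. The remaining adverse-event item that could cover the subject is the general one, which depends on the investigator's opinion that dosing cannot continue. Section 6.2.3 still calls for withdrawal without re-introduction.

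The mismatch is confined to the second case.

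It matters whether 'should' in 6.2.3 makes that rule optional. The protocol's own usage suggests not. Section 6.2.5 uses 'should' for stopping product in pregnancy, and Section 4.4.4 uses it for irreversible eGFR below 15 mL/min/1.73m². Both are also on the mandatory list in 4.4.2.

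It also matters whether the general item closes the gap. It gives the investigator a reason to record, but leaves the decision open. Section 6.2.3 leaves attribution to the investigator and then states what follows from it.

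**The case against.** The strongest reply is that nothing here is contradictory. Section 4.4.2 sets a minimum and 6.2.3 goes further for a particular event, so a site that follows 6.2.3 satisfies both. No sentence in 4.4.2 allows dosing to continue after a non-severe attributable reaction. Sites are also directed to 6.2.3 by Sections 5.6.1, 6.2.2, 6.2.2.2 and 6.2.2.3, so it is speculative to picture a site that reads 4.4.2 alone. A missing cross-reference is not unusual either, since the pancreatitis and pancreatic cancer items have none.

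Most of this stands, and it keeps the point minor. It does not remove the difference in threshold: the mandatory list names a narrower group than the section that gives the action.

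Two stronger readings are tempting, and the protocol supports neither.

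- A reader might infer that 4.4.2 permits restarting product after hypersensitivity because it states no bar. But 4.4.2 itself places no re-introduction bar on any item; the bar for confirmed pancreatitis, for instance, is in Section 3.4.1.1. Where restart is contemplated, the protocol says so: Section 4.4.3 and Appendix 4 for liver events, and Section 4.4.4 for reversible kidney injury. Section 4.4.1 exempts the listed reasons from counselling towards a temporary stop. The only statement on restart after attributable hypersensitivity is the ban in 6.2.3. Section 4.4.2 is silent, not permissive.
- A reader might infer that the withdrawal rule in 6.2.3 covers systemic reactions only. The monitoring sentence speaks of systemic manifestations, but the withdrawal sentence does not contain that limit. Writing it in could take a localized attributable reaction away from the injection site out of the present rule.

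**Conclusion.** The concern holds as a minor inconsistency in a stopping rule. For mild or moderate reactions that meet the attribution test, 6.2.3 calls for permanent withdrawal, while 4.4.2 contains no named mandatory stop.

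The consequence is for subject safety. No count can be given, because the protocol states no rate of non-severe hypersensitivity and says only that such reactions were rare in Phase III. The Phase III case cannot be placed inside or outside the gap, as its severity is not reported.

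The intention-to-treat primary analysis is unaffected, since Sections 4.4 and 4.5 keep subjects who stop product in follow-up. The 611-event target is also unaffected.

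The conclusion rests on two assumptions. First, 'Severe' in 4.4.2 carries the Appendix 5 meaning or something close to it; on any ordinary meaning, some attributable reactions fall below it. Second, the absence of a severity word in 6.2.3 is deliberate, which fits the range of reactions that section lists. The protocol does not say which threshold was intended, but taking the 6.2.3 threshold preserves the more protective rule.

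**What to change.** Leave Section 6.2.3 as it stands. In Section 4.4.2, delete the first word of the hypersensitivity item, keep its attribution wording, and add after it: (withdraw and do not re-introduce; see Section 6.2.3). Isolated injection site reactions are handled separately. The last sentence reflects 6.2.3, where injection site reactions and immunological reactions are separate adverse events of special interest. Do not add 'Systemic' to the withdrawal rule in either section.

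The cost is a wording change to one item in an amendment. The downside is possibly a few more permanent discontinuations for non-severe reactions, all of which 6.2.3 already calls for.

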4.4.3. Liver Chemistry Stopping Criteria

Liver chemistry stopping and increased monitoring criteria have been designed to assure subject safety and evaluate liver event aetiology (in alignment with the FDA premarketing clinical liver safety guidance).

[figure not shown]
<http://www.fda.gov/downloads/Drugs/GuidanceComplianceRegulatoryInformation/Guidances/UCM174090.pdf>

Phase III-IV Liver Chemistry Stopping and Increased Monitoring Algorithm

Liver safety required actions and follow up assessments section can be found in [Appendix 3](#).

Phase III-IV Liver Chemistry Increased Monitoring Algorithm with Continued Therapy for ALT $\geq 3xULN$ but $< 8xULN$

Liver Safety Required Actions and Follow up Assessments Section can be found in [Appendix 3](#).

Drug re-challenge following drug induced liver injury is not allowed.

Restart may be considered if GSK Medical Governance approval is granted (see [Appendix 4](#) for details). Restart refers to resuming study treatment following liver stopping events in which there is a clear underlying cause (other than DILI) of the liver event (e.g. biliary obstruction, pancreatic events, hypotension, acute viral hepatitis). Furthermore, there should be no evidence of alcoholic hepatitis or hypersensitivity, and the study treatment should not be associated with human leukocyte antigen (HLA) markers of liver injury.

4.4.4. eGFR Stopping Criteria

A baseline eGFR $\geq 30\text{mL}/\text{min}/1.73\text{m}^2$ is a requirement for entering the study. Subjects can continue to take investigational product if functioning well as long as eGFR is $\geq 15\text{mL}/\text{min}/1.73\text{m}^2$.

During this study, if a subject's eGFR approaches $30\text{mL}/\text{min}/1.73\text{m}^2$ closer monitoring of renal function is considered prudent, according to standard clinical practice. Particular

care should be taken to monitor renal function in subjects with renal impairment reporting severe adverse GI events. If eGRF is $<15\text{mL}/\text{min}/1.73\text{m}^2$ and considered irreversible based on consecutive measurements the investigational product should be discontinued, the subject continue in the study and be followed until the final study visit.

If eGRF is $<15\text{mL}/\text{min}/1.73\text{m}^2$ and the patient is considered to have temporary acute kidney injury that is potentially reversible, the investigational product should be temporarily discontinued until the eGRF is stable and $\geq 15\text{mL}/\text{min}/1.73\text{m}^2$. Events considered to reflect worsening renal function should be reported as SAE/AEs and targeted eCRFs completed for this AE of special interest (Section 6.2.3).

4.5. Procedures for Subject Follow-up

As described in Section 4.4, subjects who permanently discontinue investigational product will be asked to attend the clinic as soon as possible. They will continue in the study for follow-up. Five weeks (± 1 week) after discontinuation of investigational product, subjects will be contacted for a follow-up by telephone. They will be asked to return to clinic according to the 8 monthly visit schedule and in addition be contacted by telephone at a time corresponding to the 4-monthly visit they would have otherwise made to replenish study medication supply. If instead of these interim telephone contacts the subject prefers to attend clinic every 4 months as originally scheduled that is an acceptable alternative.

If a subject permanently discontinues investigational product and is unable to attend visits in-person, he/she will be contacted by telephone or other methods to assess study outcomes and vital status, unless the subject has specifically withdrawn consent for all forms of contact. Follow-up of subjects who withdraw consent for contact is described below.

Every effort should be made to educate the subjects on the importance of remaining in the study and attending scheduled study visits including those required after early discontinuation of investigational product.

Other subject follow-up options to collect study outcomes and vital status should be pursued according to local laws and regulations. If one of these alternate methods to collect study outcomes and vital status is acceptable to the subject, then the subject will be deemed not to have withdrawn consent for follow-up.

4.5.1. Withdrawal of Consent for Contact

Subjects who no longer wish to attend study visits in-person will be asked to be contacted by telephone or other methods to assess study outcomes and vital status. However, if a subject specifically withdraws consent to be contacted for additional information, no further study visits or study-related telephone contacts can be conducted. Information regarding study outcomes or vital status will continue to be collected from available sources including those in the public domain. Additionally, alternative permitted options to obtain study outcomes and vital status will be reviewed based on accepted local laws and regulations. For any subject who withdraws consent for contact, the study site will be asked to document the discussion with the subject regarding each of the contact options that were offered.

4.5.2. Subjects Deemed Lost to Follow-up

Finally, investigators should make every effort to contact subjects who are deemed lost to follow-up and who have not withdrawn consent to follow-up contacts, including pursuing any alternative contact methods permitted by local regulations. Where permitted, a third party may be used to locate alternative subject contact information that will be provided to the investigator. All attempts to contact subjects will be documented in the subject's eCRF and source notes.

Should a subject fail to attend the clinic for a required study visit, the site should attempt to contact the subject and re-schedule the missed visit as soon as possible. The site should also counsel the subject on the importance of maintaining the assigned visit schedule. In cases where the subject does not return for the rescheduled visit or cannot be reached to reschedule the missed visit, the site should make every effort to regain contact with the subject. Should the subject continue to be unreachable, then and only then will he/she be considered "Lost to Follow-up". Nonetheless, efforts to attempt to locate and contact the subject will continue until the study end.

5. STUDY TREATMENTS

5.1. Investigational Product and Other Study Treatment

Albiglutide (and albiglutide matching placebo) will be provided as a fixed-dose, fully disposable pen injector system for delivery of the investigational product (albiglutide or albiglutide matching placebo) from a prefilled dual chamber glass cartridge that is an integral part of the pen. The pen is intended for single use by the subject. It is designed for manual reconstitution of the dose, priming and insertion of the pen needle, and manual injection by the subject.

Albiglutide (or albiglutide matching placebo) is intended for self-administration as a subcutaneous injection in the abdomen, thigh or upper arm region. Rotation of use of injection sites is recommended. Albiglutide and insulin may be injected in the same body region but the injections should not be adjacent to each other. The albiglutide pen includes a mechanical locking system that prevents the user from manipulating the dose button before the cartridge has been fully reconstituted. Reconstitution is performed through rotation of the pen housing parts. The pen is designed to work with standard pen needles.

When the injector pen product is reconstituted by the subject, a neutral, isotonic solution is produced. Separate pens are required to deliver either 30 mg of albiglutide, 50 mg of albiglutide, or matching placebo in a 0.5-mL injection volume.

The contents of the label will be in accordance with all applicable regulatory requirements.

Under normal conditions of handling and administration, investigational product is not expected to pose significant safety risks to site staff. Take adequate precautions to avoid direct eye or skin contact and the generation of aerosols or mists. Notify the monitor of any unintentional occupational exposure. A Material Safety Data Sheet (MSDS)

describing the occupational hazards and recommended handling precautions will be provided to site staff if required by local laws or will otherwise be available from GSK upon request.

The investigational product (albiglutide and albiglutide matching placebo) must be stored in a secure area at 2°C to 8°C and protected from freezing. Each site must maintain a temperature log. Access to and administration of the investigational product will be limited to the investigator and authorised site staff (investigator or designee). Investigational product must be dispensed or administered only to subjects enrolled in the study and in accordance with the protocol.

Procedures for the disposal of unused study treatment will be provided in the SRM.

Investigational product (albiglutide or albiglutide matching placebo) will be administered once weekly by subcutaneous injection. The first dose is to be administered at the clinic. The starting dose of albiglutide will be 30 mg once weekly. If at any stage after 5 weeks of treatment in the opinion of the investigator the subject needs to have intensified therapy to improve glycaemic control, the dose of investigational product should be increased before altering the doses of other glucose-lowering medication. In this case the subject will be called in for an unscheduled visit to supervise an increase in dose from 30 mg to 50 mg. Subjects randomly assigned to albiglutide matching placebo will also go through the increased dose procedure to maintain study blind. If a subject experiences tolerability issues with the higher, 50mg dose then the investigator may decrease the dose back to 30 mg without the need for an unscheduled visit to supervise down titration, other than for the subject to collect pens of the correct dose.

Albiglutide (or albiglutide matching placebo) may be administered at any time of day without regard to meals. Preferably, it should be administered once a week on the same day each week. The day of weekly administration can be changed if necessary as long as the last dose was administered 4 or more days previously. If a dose is missed, it should be administered as soon as possible within 3 days after the missed dose. Thereafter, subjects can resume dosing on their usual day of administration. If it is more than 3 days after the missed dose, subjects should wait and administer their next regularly scheduled weekly dose.

If a subject misses 4 or more consecutive doses, the investigator should contact the medical monitor to discuss options for helping assure better compliance.

